In a multi-center Phase I/II trial dose-finding study (106-03), Witzig et al treated 51 patients with relapsed or refractory non-Hodgkin's lymphoma with Ibritumomab Tiuxetan (Y2B8, Zevalen®).[78] Eligibility criteria included an ANC > 1,500/mm3, platelets > 100,000/mm3 and bone marrow involvement < 25%. Median age was 60 years. Patients had a median of two prior regimens (range, 1-7). In the phase I portion of the trial, patients received either 100 or 250 mg/m2 of unlabeled rituximab (to clear peripheral B-cells and improve biodistribution) followed by Indium-111ibritumomab tiuxetan (5 mCi on Day 1 for imaging and Y-90-ibitumomab tiuxetan 0.2, 0.3, or 0.4 mCi/kg on Day 8. The optimal dose of unlabeled rituximab was determined to be 250 mg/m2 and 0.4 mCi/kg was the maximally tolerated dose of Yttrium-90. In an intent-to- treat analysis the overall response rate was 67%, including 26% CRs and 41% PRs. Thirty-four patients with low grade lymphoma achieved an 82% overall response rate (26% CRs, 56% PRs), 43% of 14 aggressive lymphomas responded, and none of the three patients with mantle cell disease responded. Estimated time to progression for intent to treat was 12.9 months and estimated median duration of response was 11.7 months. Hematologic toxicity was dose-limiting. Thrombocytopenia was the most common hematologic event. Hematologic toxicity was transient and reversible. Only one patient developed an immune response.

Witzig et al $^{[79,80]}$ (106-04) conducted a randomized phase III trial in 143 patients with relapsed or refractory low-grade, follicular, or CD 20+ transformed NHL. Patients received either ibritumomab tiuxetan, 0.4 mCi/kg (maximum of 32 mCi) or rituximab, 375 mg/m2 weekly for 4 weeks. Eligibility required an ANC \geq 1,500/mm3, a platelet count \geq 100,000/mm3, and bone marrow involvement < 25%. As assessed by International Workshop Response Criteria, $^{[81]}$ patients who received ibritumomab tiuxetan achieved an overall response rate (ORR) of 80% (73 patients) compared with 56% (70 patients) for patients on the rituximab arm (p = 0.002). Complete response (CR) rates were 30% for the ibritumomab tiuxetan group and 16% for the rituximab group (p = 0.04), with an additional 4% of

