For the purpose of toxicity assessment, the treatment period will include the time from the first ESHAP infusion to 30 days following Zevalin infusion. Evaluations during the 2 cycles of ESHAP are outlined in Appendix A.

5.B.1 ESHAP Cycle 1, Day 1

a. Begin ESHAP Treatment (Please refer to Section 7A for ESHAP administration)

5.B.2 ESHAP Cycle 2, Day 1

- a. History & Physical examination, including vital signs (BP, temperature & pulse), height, weight, Body Surface Area (BSA), and performance status (Appendix B).
- b. Laboratory tests including:
 - Complete blood count (CBC) with differential and platelet count
 - Serum chemistries BUN, creatinine
- c. Toxicity Assessment: Adverse events are to be recorded on an ongoing basis and on appropriate source documents at the clinical site and in the patient's case report form.

5.B.3 ESHAP Cycle 2, Day 29

- a. History & Physical examination, including vital signs (BP, temperature & pulse), height, weight, Body Surface Area (BSA) & performance status (Appendix B).
- b. Laboratory tests including:
 - Complete blood count (CBC) with differential and platelet count
 - Serum chemistries BUN, creatinine
- c. Unilateral or Bi-lateral bone marrow biopsy and aspirate for histology and determination of percent bone marrow involvement
- d. Bone marrow cytogenetics. Does not have to be done at each Bone Marrow biopsy and aspirate, but does need to be completed at either, Baseline or Cycle 2, Day 29.
- e. Disease Assessment:
 - Total of all measurable indicator lesions.
 - CT or PET scan of the chest, abdomen and pelvis
- f. Toxicity Assessment: Adverse events are to be recorded on an ongoing basis and on appropriate source documents at the clinical site and in the patient's case report form.

5.C Evaluations During the Zevalin Imaging & Treatment Period

Ibritumomab Tiuxetan Indium (111 In Zevalin) regimen is administered 4 – 6 weeks after completion of ESHAP.

5.C.1 Day 1

- a. History & Physical examination, including vital signs (BP, temperature & pulse), height, weight, Body Surface Area (BSA), and performance status are to be performed within 28 days of Rituximab & Zevalin administration. (Appendix B).
- b. Toxicity Assessment: Adverse events are to be recorded on an ongoing basis and on appropriate source documents at the clinical site and in the patient's case report form.
- c. Laboratory tests including:
 - Complete blood count (CBC) with differential and platelet count
 - Serum chemistries BUN, creatinine

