➤ Altered biodistribution

- Intense localization of radiotracer in the liver and spleen and bone marrow indicative of reticuloendothelial system uptake
- Increased uptake in normal organs (not involved by tumor) such as:
 - o Diffuse uptake in normal lung more intense than the liver.
 - o Kidneys with greater intensity than the liver on the posterior view.
 - o Fixed areas (unchanged with time) of uptake in the normal bowel greater than uptake in the liver.
 - o In less than 0.5% of patients receiving ¹¹¹In Zevalin (Ibritumomab Tiuxetan Indium), prominent bone marrow uptake was observed, characterized by clear visualization of the long bones and ribs.

If a visual inspection of the gamma images reveals an altered biodistribution, the patient should not proceed to the ⁹⁰Y Zevalin (Ibritumomab Tiuxetan Ytrium-90) dose. The safety and efficacy of the administration of ⁹⁰Y Zevalin (Ibritumomab Tiuxetan Ytrium-90)in patients with prominent marrow uptake is not known. Possible causes of prominent bone marrow uptake, such as bone marrow involvement by lymphoma, increased marrow activity due to recent hematopoietic growth factor administration, and increased reticuloendothelial uptake in patients with HAMA and HACA, should be considered. Re-assessment of biodistribution after correction of underlying factors should be performed. ⁹⁰Y Zevalin (Ibritumomab Tiuxetan Ytrium-90) should not be administered to patients with persistently prominent marrow uptake on the repeat biodistribution scans.

5.C.3 Day 7, 8 or 9

a. Rituximab Infusion & ⁹⁰Y Zevalin (Ibritumomab Tiuxetan Ytrium-90) Infusion (Please refer to section 7.B for detailed treatment administration)

5.C.4 Day 35 (+/- 7 days)

a. Laboratory tests including:

Complete blood count (CBC) with differential and platelet count. To be done every week until any count abnormalities have passed nadir.

5.D Restaging

5.D.1 3 Months Post-90Y Zevalin (Ibritumomab Tiuxetan Ytrium-90) Infusion

The following tests/evaluations will be obtained 3 months (+/- 7 days) post ⁹⁰Y Zevalin Infusion:

- a. History & Physical examination, including vital signs (BP, temperature & pulse), height, weight, Body Surface Area (BSA) & performance status (Appendix B).
- b. Laboratory tests including:
 - Complete blood count (CBC) with differential and platelet count
 - Serum chemistries BUN, creatinine
 - LDH
- c. Disease Assessment:
 - Total of all measurable indicator lesions.
 - CT or PET scan of the chest, abdomen and pelvis

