All Grade 3 and 4 events occurring in < 5% of patients (except for those noted in Table 5) consisted of pancytopenia (1.7%), allergic reaction (1.1%), dehydration (1.1%), gastrointestinal hemorrhage (0.9%), hyperglycemia (0.9%), melena (0.9%), tumor pain (0.9%), increased alkaline phosphatase (0.6%), ascites (0.6%), constipation (0.6%), increased lactic dehydrogenase (0.6%), increased SGPT (0.6%), malaise (0.6%), apnea (0.6%), bilirubinemia (0.6%), hypoxia (0.6%), deep thrombophlebitis (0.6%), hypochromic anemia (0.3%),angioedema (0.3%),anxiety (0.3%), depression (0.3%),hypoproteinemia (0.3%), increased SGOT (0.3%), insomnia (0.3%), neck pain (0.3%), pleural effusion (0.3%), somnolence (0.3%), tachycardia (0.3%), urticaria (0.3%), anemia hemolytic (0.3%), arterial anomaly (0.3%), arrhythmia (0.3%), arthritis (0.3%), cachexia (0.3%), convulsion (0.3%), coronary artery disorder, (0.3%), easy bruisability (0.3%), lung edema (0.3%), pulmonary embolus (0.3%), encephalopathy (0.3%), granulocytosis (0.3%), congestive heart failure (0.3%), hematemesis (0.3%),

subdural hematoma (0.3%), hepatic failure (0.3%), hypercalcemia (0.3%), hyperuricemia, (0.3%), increased prothrombin (0.3%), myocardial ischemia (0.3%), jaundice (0.3%), kidney failure (0.3%), migraine (0.3%), neuritis (0.3%), intestinal obstruction (0.3%), eye pain (0.3%), respiratory disorder (0.3%), supraventricular tachycardia (0.3%), vaginal hemorrhage (0.3%), and increased venous pressure (0.3%).

Hematologic Events: Hematologic toxicity has been frequently observed in clinical trials, and is dose-limiting. Table 6 presents the incidence and duration of Grade 3 and 4 hematologic toxicity for patients with mild thrombocytopenia at baseline who were treated at 0.3 mCi/kg (11.1 MBq/kg), and for those with normal baseline platelet count treated at 0.4 mCi/kg (14.8 MBq/kg), up to the maximum dose of 32 mCi (1184 MBq).

Table 6 Hematologic Toxicity

	Median Nadir	Patients with Grade 3 Toxicity	Patients with Grade 4 Toxicity	Days Within Grade 3 or 4* (Median for all Patients)	Days Within Grade 3 or 4* (Median for Patients with Grade 3 or 4 Nadir)	
0.3 mCi/kg; 11.1 MBq/kg dose (maximum 32 mCi; 1184 MBq)						
ANC (cells/mm ³)	600	40%	35%	23.0	29.0	
Platelets (/mm³)	24,000	66%	14%	29.0	34.5	
Hemoglobin (g/dL)	10.0	12%	8%	0.0	14.0	
0.4 mCi/kg; 14.8 MBq	/kg dose (m	aximum 32 m	Ci; 1184 MB	q)		
ANC (cells/mm³)	800	28%	30%	14.0	22.0	
Platelets (/mm ³)	41,000	52%	10%	15.0	24.0	

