12 STATISTICAL CONSIDERATIONS

12.A Study Design

This is a two- institution phase II trial to determine the efficacy and safety of the ESHAP-Zevalin combination therapy for the management of relapsed (CD 20+) follicular lymphoma. Patients must have received at least one, but no more than 2 prior treatments for follicular lymphoma.

The primary objective of this phase II clinical trial is to evaluate the 1-year progression-free survival (PFS) of patients with relapsed follicular NHL treated with ESHAP chemotherapy for cytoreduction (2 cycles) followed by Y-90 ibritumomab tiuxetan (Zevalin) radioimmunotherapy, compared to what would be expected historically for patients treated with Zevalin without prior cytoreduction. For this patient population, a 1-year PFS of 67.3% will be considered highly encouraging, compared to an historical rate around 50%. These values correspond to approximate median times to progression of 21 months and 12 months, respectively, assuming exponential survival.

12.B. Sample Size

The planned sample size of 52 evaluable patients is based on testing the null hypothesis that the true 1-year PFS is \leq 50%, versus an alternative hypothesis that the true rate is \geq 67.3% with this therapeutic approach. Based on the number of patients seen at the Arizona Cancer Center with relapsed follicular lymphoma requiring treatment, the anticipated accrual rate is 2 patients per month. It is estimated that accrual to the study would be completed within 26 months. All patients who receive at least one dose of chemotherapy will be considered evaluable and included in the analysis. In the unlikely event that an enrolled patient does not receive treatment, an additional patient will be registered.

12.C Method of Analysis

The following are the design characteristics based on a chi-square test for one binomial population at the one-sided 0.10 significance level. If the true PFS is $\leq 50\%$, then there is a maximum probability of 0.10 of concluding that this treatment approach is sufficiently promising that it should be accepted for further study (false positive rate). Alternatively, if the true PFS is $\geq 67.3\%$, then the maximum probability of

rejecting this treatment approach for further study in this setting is 0.10 (false negative rate), equivalent to a power of 90%.

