APPENDIX A

STUDY CALENDAR

4/1/2010

STUDY CALENDAR Page 1

					Ibritumomab Tiuxetan (Zevalin)			
Required Studies	Baseline	ESH	AP Treatm	ent		Regin	nen [∞]	
Visits (weeks or days)	Within28 days prior to C1, D1	Cycle 1 Day 1	Cycle 2 Day1	Cycle 2 Day 29	Day 1	Day 2,3,4,5	Day 7, 8, or 9	Day 35
PHYSICAL								
History / Physical / vital signs ^α	X		X	X	ΧП			
Height / Weight / BSA / PS	X		X	X	ΧП			
Disease Assessment	X			X				
Toxicity Assessment	X		X	X	ΧП			
LABORATORY								
CBC / differential / platelets	X		X	X	ΧП			\mathbf{X}^{Σ}
Serum Creatinine / BUN	X		X	X	ΧП			
AST/ ALT/ Alk. Phos/ T. Bilirubin^	X							
LDH	X							
BHCG [†]	X							
Beta 2- microglobulin	X							
Hepatitis B screen*	X							
Pathology Review [£]	X							
Bone marrow cytogenetics [¥]	X			X				
Bone marrow aspiration and Bx	X			X				
SCANS								
CT or PET Chest	X			X				
CT or PET Abdomen	X			X				
CT or PET Pelvis	X			X				
Gamma Scan						X≠		
TREATMENT								
ESHAP		X	X					
Rituximab 250 mg/m2					X		X	
Ibritumomab Tiuxetan Indium (¹¹¹ In Zevalin)					X			
Ibritumomab Tiuxetan Ytrium-90 (90Y Zevalin)							X	

- α Vital Signs consist of BP, temperature and pulse
- t Baseline for women of childbearing potential
- ¥ A scan is performed at 48-72 hours after 111In Zevalin. Another optional scan may be performed at 90-120 hours after 111In Zevalin.
- ∞ ¹¹¹In Zevalin is administered 4-6 weeks after completion of ESHAP.
- ٨ Required at Baseline and Encouraged to repeat as clinically indicated by Good Medical Practice.
- Encouraged by Good Medical Practice, but not required.
- ¥ Bone Marrow cytogenetics can be done at either Baseline or C2,D29, but must be done at least once.
- £ Pathology Review consists of a basic review of a pathology report. If possible submit: Representative H&E stained slides from the diagnostic biopsy, one representative paraffin block and one copy of the pathology report.
- Σ Starting Day 35 (+/- 7 days) a CBC w/ Diff and Platelet count should be done every week until nadir.
- Within 28 days prior to Rituximab & Zevalin administration..

STUDY CALENDAR Page 2

Required Studies	Restaging	Short-Term Follow-Up				Long-Term Follow-Up	Off-Study [#]
Visits (weeks or days)	3 mos post ⁹⁰ Y Zevalin	6 mos post Zevalin	12 mos post Zevalin	18 mos post Zevalin	24 mos post Zevalin	Follow-Up: Annually for 3 years [£]	Disease Progression or Removed from Study (within 4 weeks)
PHYSICAL							
History / physical / vital signs ^α	X	X	X	X	X	X	X

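### The 30-day toxicity period in 5.B has no stated anchor and closes within days of the first required post-90Y blood count, so it should not define haematologic toxicity

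*Combined protocol and SAP*

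**What the plan says.** Section 5.B gives the only period that the protocol defines for toxicity: "For the purpose of toxicity assessment, the treatment period will include the time from the first ESHAP infusion to 30 days following Zevalin infusion". Two infusions fit that description. In 5.C.1 and 5.C.3, 111In Zevalin is given on Day 1 of the Zevalin regimen and 90Y Zevalin on Day 7, 8 or 9.

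The next required blood count is in Section "5.C.4 Day 35 (+/- 7 days"), with the instruction "To be done every week until any count abnormalities have passed nadir". The study calendar in Appendix A is slightly different: from Day 35, "a CBC w/ Diff and Platelet count should be done every week until nadir". After that, the next required count is at the 3-month restaging visit (5.D.1).

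Section 6.C.6 says of Zevalin: "Hematologic toxicity has been frequently observed in clinical trials, and is dose-limiting". Table 6 there gives nadir depth, grade and duration, but no day of onset or nadir.

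Section 12.A describes the trial as one "to determine the efficacy and safety of the ESHAP-Zevalin combination therapy". The end-of-trial reporting in 12.C covers PFS and response. Section 12 contains no toxicity table and does not say which period toxicity rates cover.

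**The concern.** The defined toxicity period and the blood count schedule do not fit together. The period ends at about the time the plan starts looking for the nadir, and the weekly follow-up counts run on after it has closed. A reader preparing the safety summary would naturally take the one period labelled as being for toxicity assessment. For the dose-limiting toxicity, that choice would set aside counts that the protocol itself requires.

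The undefined anchor makes this worse, because the two readings differ by 6 to 8 days, about the spacing between weekly counts. Two analysts could report different Grade 3-4 rates from the same patients, and each could cite the protocol. The primary PFS test is not affected. What is at stake is the haematologic safety profile of giving 90Y Zevalin after two cycles of ESHAP, which is part of the design aim in 12.A.

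**Working it through.** **Inputs.** Period length of 30 days (5.B); 111In on Day 1 and 90Y on Day 7, 8 or 9 (5.C.1, 5.C.3); first count on Day 35 +/- 7, i.e. Day 28 to 42, then weekly (5.C.4, Appendix A); Grade 3-4 durations (Table 6). The plan states no figure of its own on this point to reproduce.

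**Step 1: when the period closes.** Closing day = anchor day + 30.
- 90Y anchor: 7 + 30 = 37, 8 + 30 = 38, 9 + 30 = 39.
- 111In anchor: 1 + 30 = 31.

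**Step 2: when the first count falls.** Days after 90Y = count day minus 90Y day.
- Nominal: 35 - 9 = 26 to 35 - 7 = 28 days after 90Y, which is 2 to 4 days before a 90Y-anchored period closes.
- Over the allowance: 28 - 9 = 19 to 42 - 7 = 35 days.

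**Step 3: required weekly counts on or before the closing day.**

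| Reading | First count Day 28 | Day 35 | Day 42 |
|---|---|---|---|
| 90Y anchor, closes Day 37-39 | 2 | 1 | 0 |
| 111In anchor, closes Day 31 | 1 | 0 | 0 |
| Day 35 itself counted from 90Y, period 30 days from 90Y | 1 | 0 | 0 |

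The calendar numbers Day 35 in the same series as Days 1 to 9, so the first two rows are the natural readings. The third is a sensitivity check.

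**Step 4: duration.** Table 6 gives these median days in Grade 3-4 among patients with a Grade 3 or 4 nadir. The latest onset that keeps the median inside 30 days is 30 minus the median.

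| Stratum | Median days | Latest onset after 90Y |
|---|---|---|
| ANC, 0.4 mCi/kg | 22.0 | day 8 |
| Platelets, 0.4 mCi/kg | 24.0 | day 6 |
| ANC, 0.3 mCi/kg | 29.0 | day 1 |
| Platelets, 0.3 mCi/kg | 34.5 | none (34.5 > 30) |

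Section 7.B.3 does not allow 90Y with platelets below 100,000/mm³, and Table 6 sets Grade 3-4 platelets at below 50,000/mm³. These platelet episodes therefore begin after 90Y. If Table 6 carried over to this trial, at least half of the affected patients at 0.3 mCi/kg would have at least 34.5 - 30 = 4.5 Grade 3-4 platelet days beyond the period, whatever the onset day.

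**Step 5: dependence on onset (assumption).** The documents give no time to onset or nadir, so a range is shown. With onset *o* days after 90Y and duration *D*, the share of Grade 3-4 days inside the period is max(0, min(*D*, 30 - *o*)) / *D*. For *D* from 22 to 34.5 days:

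| Onset after 90Y | Share inside |
|---|---|
| day 7 | 67-100% |
| day 14 | 46-73% |
| day 21 | 26-41% |
| day 28 | 6-9% |
| day 35 | 0% |

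**Step 6: what cannot be computed.** Adding Grades 3 and 4 in Table 6 gives 28 + 30 = 58% (ANC) and 52 + 10 = 62% (platelets) at 0.4 mCi/kg, and 40 + 35 = 75% and 66 + 14 = 80% at 0.3 mCi/kg. Applied to 52 patients, this is 52 x 0.58 = 30 to 52 x 0.80 = 42. That is the number expected to have a Grade 3-4 event if all 52 received 90Y, and the upper end needs all of them to be in the 0.3 mCi/kg stratum. It is not the number missed. The 52 are patients with at least one ESHAP dose (4.C), and some will not reach 90Y (3.A, 7.B.2, 7.B.3).

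**The case against.** The strongest reply is that nothing is lost, because recording does not stop at day 30. Section 9 has every adverse event recorded with its duration and intensity, and its 30-day limit applies only once other anti-cancer therapy has begun. Toxicity is assessed again at 3 months (5.D.1) and at each later visit in Appendix A, and 5.F.1 follows events in off-study patients until they settle or are judged permanent. No passage confines a safety table to the 5.B period, and an episode that starts inside the period could keep its full duration. All of this stands. It shows that the data will exist, but not which data enter the summary: the plan has a bounded toxicity period beside open-ended recording, and no rule linking them.

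A reader might infer two stronger things. One is that the nadir falls largely outside the period. The documents do not support this. Table 6 is silent on timing, the background says only "Hematologic toxicity was transient and reversible", and weekly counting until the nadir has passed fits a nadir at or before Day 35 as well as a later one. By Step 5, most Grade 3-4 time lies outside only for onset from about the third week after 90Y. The other is that toxicity is under-counted. That follows only if the summary is restricted to the 5.B period, which is possible but not stated.

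It can also be said that 30 days matches Table 5. That is true, but Table 5 leaves out neutropenia, thrombocytopenia and anaemia, so it is a precedent for non-haematologic events only. The infection summary in 6.C.6 uses the first 3 months.

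**Conclusion.** The point holds in a conditional form. The 5.B period has an undefined anchor and is out of step with the count schedule: one required post-90Y count inside on the nominal 90Y reading (range 0 to 2), and none on the nominal 111In reading. If haematologic toxicity is tabulated within it, worst grades first seen on later scheduled counts are dropped. Grade 3-4 time is truncated if only days inside the period are counted; the 34.5-day platelet median at 0.3 mCi/kg exceeds the 30 days available.

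The day arithmetic rests only on the protocol. The duration argument assumes that Table 6, which comes from Zevalin trials rather than from patients given ESHAP first, carries over. The number of patients affected is unknown and cannot be derived from these documents. This is a cheap improvement: a stated rule that could remove required data on the dose-limiting toxicity, repairable by wording.

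**What to change.** In 5.B, state that the anchor is 90Y Zevalin, or 111In Zevalin for patients who do not go on to 90Y. Define the haematologic toxicity reporting period as first ESHAP infusion through the 3-month post-90Y restaging visit, including every weekly CBC. Report the worst haematologic grade over that period among patients given 90Y.

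Report duration only as bounded by the available counts. Weekly counts are required until the nadir has passed, not until recovery, so the end of an episode may be known only to lie between the last weekly count and the 3-month count.

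Keep the 30-day period for non-haematologic events, so that they stay comparable with Table 5. Add the safety reporting period to Section 12, so that the choice is fixed before the data are seen.

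The cost is protocol wording. The counts and the 3-month toxicity assessment are already scheduled, and worst grade needs no extra visit. The downside is that reported haematologic toxicity may look higher than under a 30-day rule.

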3 STUDY DESIGN

3.A Treatment Summary

After informed consent has been obtained, patients will undergo screening to assure eligibility for the study. After two cycles of ESHAP have been given, patients will be restaged to determine response. Patients with residual involvement of more than 25% of bone marrow after the two cycles of ESHAP will be taken off treatment and followed for time to progression and survival. Patients experiencing disease stabilization or reduction with less than 25% residual bone marrow involvement will undergo imaging for biodistribution. If biodistribution is acceptable, then patients will receive the Zevalin treatment and undergo a second disease evaluation for response assessment. Thereafter, patients will be followed at 6 month intervals (Short-term follow-up) for 2 years, and then annually (Long-Term follow-up) for an additional 3 years

3.B Study Duration

The estimated active accrual period for this study is 5 years. After completion of treatment, patients will be followed for 5 years to allow determination of study endpoints.

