- d. Toxicity Assessment: Adverse events are to be recorded on an ongoing basis and on appropriate source documents at the clinical site and in the patient's case report form.

5.E Follow-Up Evaluations

5.E.1 Short-Term Follow-Up Period

- a. The following tests/evaluations will be obtained at 6-month intervals (+/- 7 days) for a period of 2 years (24 months) following the Zevalin:
 - History & Physical examination, including vital signs (BP, temperature & pulse), height, weight, Body Surface Area (BSA), and performance status (Appendix B).
 - Laboratory tests including:
 - o Complete blood count (CBC) with differential and platelet count
 - o Serum chemistries BUN, creatinine
 - o LDH
 - Disease Assessment (Only required at 6-month intervals for a period of 2 years (24 months) following Zevalin):
 - o Total of all measurable indicator lesions.
 - CT or PET scan of the chest, abdomen and pelvis (Restaging of disease by CT scan is recommended every 6 months up to Month 24, then annually until year 5).

5.E.2 Long-Term Follow-Up Period

- a. The following tests/evaluations will be obtained annually (+/- 30 days) for an additional 3 years after the completion of the Short-Term Follow-Up period:
 - History & Physical examination, including vital signs (BP, temperature & pulse), height, weight, Body Surface Area (BSA), and performance status (Appendix B).
 - Laboratory tests including:
 - o Complete blood count (CBC) with differential and platelet count
 - o Serum chemistries BUN, creatinine
 - LDH
 - Disease Assessment:
 - o Total of all measurable indicator lesions.
 - o CT or PET scan of the chest, abdomen and pelvis

Once the patients have completed the Short-Term Follow-Up period they will continue to be followed for 3 years on an annual basis (+/- 30 days) for survival and disease status. Patients should be followed by physical exam and, if clinically indicated by Good Medical Practice, CT or PET scans. Patients will be followed for 3 years or until patient starts alternate treatment or is removed from study to allow determination of study endpoints.

5.F Disease Progression Evaluations/Off-Study

Patients who develop disease progression during the treatment period and who do not begin other anti-cancer therapy will continue to be followed for routine safety and efficacy for a total of 30 days following any discontinuation of treatment for any cause.

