Study-specific data forms are to be found in the Clinical Research Services clinical database. All forms are to be submitted centrally to the Clinical Research Coordinator at the University of Arizona Cancer Center at baseline, completion of ESHAP cycle 1, completion of ESHAP cycle 2, restaging at Cycle 2, Day 29, completion of Zevalin®, and at the follow-up intervals specified in Appendix A, including at time of relapse/progression, second malignancy, or death.

13.D Patient Confidentiality

The information obtained as a result of this research is confidential and all efforts must be made to ensure that the patient's anonymity will be maintained. All records, evaluation forms, and reports will be identified by an identification code to maintain confidentiality. A log of patients' codes, names and addresses will be kept separately. All records are to be kept in locked files.

13.E Monitoring

This research study is an investigator-sponsored trial. The Arizona Cancer Center has an NCI-approved Data and Safety Monitoring Plan for clinical research. Data and systems for participating in the study will be monitored according to procedures outlined in that plan, with centralized patient screening and registration, submission and review of data, and initial verification of data as summarized below.

Protocol Data and Safety Monitoring Plan (Medium Risk)

Medium risk studies are intended to include all trials involving therapeutic intervention(s), which are **not** designated as high risk per NCI and the IND is not held by the investigator.

Data and Safety Monitoring Plan:

1. Identification of the DSMB obligated for oversight responsibilities:

The Arizona Cancer Center Data and Safety Monitoring Board (DSMB) will provide ongoing oversight for this trial.

2. Identification of the entity obligated for routine monitoring duties:

Routine monitoring will be provided by the Quality Assurance/Quality Control (QA/QC) Program to ensure that the investigation is conducted according to protocol design and regulatory requirements.

3. Monitoring progress and data review process:

Routine monitoring of subject data will be conducted at least every six months.

The first routine monitoring visit will include at a minimum:

• Informed consent – 100% of cases enrolled;

- Subject eligibility 50% of cases, up to two subjects;
- Data review 50% of cases, up to two subjects.

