Height/Weight /BSA/PS	X	X	X	X	X	X	X
Disease Assessment	X	X		X		X	X
Toxicity Assessment	X	X	X	X	X	X	X
LABORATORY							
CBC/differential/platelets	X	X	X	X	X	X	X
Serum Creatinine/BUN	X	X	X	X	X	X	X
LDH	X	X	X	X	X	X	X
X-RAYS AND SCANS							
CT or PET chest	X	X		X		X	X
CT or PET Abdomen	X	X		X		X	X
CT or PET pelvis	X	X		X		X	X

- Ω After completion of post Zevalin restaging, follow-up exams and tests are to be repeated every 6 months for 2 years, and then annually for up to 3 years.
- # Off-Study Tests to be Performed When a Patient is Determined to Have Disease Progression or is Removed from the Study for any Reason. These tests will be performed within 4 weeks after a patient has demonstrated progression of disease, or removed from study. These tests do not have to be repeated if they were performed within 7 days prior to documentation of disease progression.
- α Vital signs consist of BP, temperature and pulse
- Follow-up should occur every 6 months (+/- 30 days) for 2 years after the completion of the Short-Term Follow-Up period.
- £ Continued Follow-Up should occur annually (+/- 30 days) for survival and disease status. Patients should be followed by physical exam and, if clinically indicated by Good Medical Practice, CT scans. Patients will be followed for 3 years or until patient starts an alternate treatment or is removed from study to allow determination of study endpoints.

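### Appendix A leaves the 12- and 24-month disease assessments blank although 5.E.1 requires them, and Section 12 does not state when the 1-year PFS clock starts

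*Combined protocol and SAP*

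**What the plan says.** **Schedule in the text.** Section 5.E.1 sets "Disease Assessment (Only required at 6-month intervals for a period of 2 years (24 months) following Zevalin". The imaging line in the same list is softer: "Restaging of disease by CT scan is recommended every 6 months up to Month 24, then annually until year 5". Section 3.A agrees on the interval: "patients will be followed at 6 month intervals (Short-term follow-up) for 2 years".

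**Schedule in the calendar.** The short-term columns on page 2 of Appendix A are "6 mos post Zevalin 12 mos post Zevalin 18 mos post Zevalin 24 mos post Zevalin", with a 3-month restaging column before them and long-term and off-study columns after. The assessment row reads "Disease Assessment X X X X X": five marks over seven columns, at 3, 6 and 18 months, long-term and off-study. The CT/PET rows for chest, abdomen and pelvis have the same pattern. A footnote on that page says "follow-up exams and tests are to be repeated every 6 months for 2 years". Section 13.C makes data forms due "at the follow-up intervals specified in Appendix A, including at time of relapse/progression".

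**Origin of the endpoints.** Sections 2.A.1 and 2.A.2 make 1-year PFS and median TTP both primary. Section 12 gives no starting point for 1-year PFS. Appendix D, Table 2, which reports a workshop's recommended definitions, counts PFS from trial entry. Appendix D, section 2, counts TTP from first study treatment and dates progression when it is documented. Section 12.A nevertheless converts one endpoint into the other: "These values correspond to approximate median times to progression of 21 months and 12 months, respectively, assuming exponential survival".

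**Patients without 90Y Zevalin.** Section 3.A keeps patients with too much residual marrow disease in follow-up for TTP and survival. Sections 6.C.5 and 7.B.2 take patients with altered biodistribution off study. Section 4.C counts everyone given one dose of ESHAP as evaluable.

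**The concern.** The grid contradicts both the text and its own footnote about when progression is looked for. Because progression is dated when documented, a missing scan moves the recorded date to the next scan or to clinical discovery. The stretch the grid leaves empty contains month 12 from first treatment, the null value for median TTP.

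The origin is a second, separate gap. PFS from entry, TTP from first ESHAP and scans counted from Zevalin are three clocks, and Section 12 does not say which one defines 1 year. Patients who never receive 90Y Zevalin have no date from which later scans can be scheduled, yet they count in the analysis.

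**Working it through.** **1. The plan's own figures.** With one-sided alpha 0.10, power 90%, p0 = 0.50 and p1 = 0.673 (12.B, 12.C):

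n = [1.2816·√(0.5·0.5) + 1.2816·√(0.673·0.327)]² / 0.173² = 51.54, rounded up to 52.

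The conversion in 12.A also holds: 0.5^(12/21) = 0.673. Neither figure is in dispute.

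**2. Where Zevalin falls, counting first ESHAP (C1D1) as day 1.** Inputs are the 28-day cycles, the 4-6 week interval and 90Y on Day 7-9 (7.A, 7.B), and a cycle-2 delay of up to two weeks (8.A.1).

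- Earliest: last ESHAP dose on day 32, + 28 = day 60; 90Y on regimen Day 7 = day 66. That is 65 days, or 2.1 months.
- Latest: cycle 2 ends on day 56, + 42 = day 98; 90Y on regimen Day 9 = day 106; + 14 days of delay = day 120. That is 119 days, or 3.9 months.

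**3. Post-Zevalin scans, in months from first ESHAP.**

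| Scan after Zevalin | From first ESHAP | 5.E.1 | Grid |
|---|---|---|---|
| 6 months | 8.1-9.9 | yes | yes |
| 12 months | 14.1-15.9 | yes | blank |
| 18 months | 20.1-21.9 | yes | yes |
| 24 months | 26.1-27.9 | yes | blank |

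**4. Effect on median TTP (scenario).** Assume exponential TTP with a true median of 12 months, S(t) = 0.5^(t/12), and Zevalin at month 3. A fraction f of progressions after the month-9 scan is found clinically when it occurs; the rest wait for the next scan, at month 15 (5.E.1) or month 21 (grid). S(9) = 0.5946. Until the next scan the observed curve is (1−f)·S(9) + f·S(t). Setting it to 0.5 gives t; if it has not reached 0.5 by the next scan, it drops below 0.5 there, since S(15) = 0.42 and S(21) = 0.30.

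| f | Median under 5.E.1 | Median under grid |
|---|---|---|
| 0.90 | 12.4 | 12.4 |
| 0.75 | 13.1 | 13.1 |
| 0.50 | 15 | 15.6 |
| 0 | 15 | 21 |

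For f = 0.5, for example: S(t) = (0.5 − 0.2973)/0.5 = 0.4054, so t = 15.6. With f = 0 and Zevalin anywhere between 2.1 and 3.9 months, the observed median is 14.1-15.9 under 5.E.1 and 20.1-21.9 under the grid.

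**5. Effect of the blanks on 1-year PFS.** From first ESHAP, the last scan before month 12 is the 6-month post-Zevalin scan (8.1-9.9) and the next is at 14.1 or later. If entry is assumed to be 28 days before C1D1, these become 9.1-10.8 and 15.1 or later. Under both origins the restored 12-month scan falls after the landmark, so the blanks change nothing at 1 year.

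**The case against.** The strongest reply is that this is a clerical slip. The footnote and 5.E.1 both call for six-monthly tests, the 12- and 24-month columns still exist (so forms are still due under 13.C), and those visits keep history, examination and LDH. All of that stands. It makes the matter a contradiction to reconcile, not evidence of a decision to omit the scans. But sites often work from the grid, and four rows share the same blanks, so a fault in text extraction is unlikely. The strict conflict is over the disease assessment, because 5.E.1 only recommends CT restaging.

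It is also fair to say that the origin is not absent from the document, since Appendix D has one for each endpoint. What remains is that Section 12 cites neither, and they differ.

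A reader might infer more: that the blanks inflate the false-positive rate of the 1-year PFS test. With a Zevalin origin and a 31/52 cut-off, scenario rates of 17%, 31%, 60% and 97% follow for f = 0.9, 0.75, 0.5 and 0. No passage gives a Zevalin origin, and it fits poorly with counting every ESHAP-treated patient as evaluable.

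A second tempting reading is that 1-year PFS is biased upward even under 5.E.1, because no scan falls at month 12 from first ESHAP. For the same values of f, with Zevalin at month 3, scenario false-positive rates are 13%, 18%, 29% and 55% at 31/52 (nominal 10.6%), but 8%, 12%, 20% and 44% at 32/52 (nominal 6.3%). The documents do not give the share found clinically. The historical 50% is also an observed rate with an unknown scan schedule: if it carried a 3-month lag with the same detection, the excess would be nil. The net direction against the benchmark is therefore not established.

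**Conclusion.** The contradiction is real and should be corrected. If the grid is followed, no scan is scheduled between 6 and 18 months after Zevalin, and progressions around the 12-month null median TTP could be dated late. At worst the observed median is about 21 months instead of 15. The difference shrinks to 0.6 months when half of the progressions are found clinically and vanishes at three quarters. These figures assume exponential TTP, Zevalin at month 3 and documentation-based dating; the true share found clinically is unknown. The formal test in 12.C is on 1-year PFS, so this affects the estimate of a primary objective and not that test.

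The missing origin in Section 12 is a separate defect of specification. Under either origin in Appendix D the blanks leave 1-year PFS unchanged, and the size and net direction of any scan-timing bias against the historical 50% cannot be determined from the documents.

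**What to change.** 1. On page 2 of Appendix A, mark disease assessment and CT/PET of chest, abdomen and pelvis in the 12- and 24-month columns, so that the grid agrees with 5.E.1 and its own footnote.
2. In Section 12, state one origin for both 1-year PFS and TTP. First ESHAP dose is a natural choice: it is already the TTP origin and every evaluable patient has one. Align the PFS row of Appendix D, Table 2.
3. Reconcile 3.A, 4.C, 6.C.5 and 7.B.2 on how evaluable patients who never receive 90Y Zevalin are followed, and state in Section 12 how their 1-year status is scored.

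The follow-up visits should not be re-timed from Zevalin to first ESHAP on this account. That would end six-monthly post-Zevalin imaging earlier and add scan visits for patients never given Zevalin, to address a bias whose net direction is unknown.

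Cost: items 1 and 2 are calendar and wording changes, with two scan visits more than the printed grid and none beyond 5.E.1. The cost of item 3 depends on how those passages are reconciled. N stays 52.
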